5.2 Exclusion criteria

Participants meeting **any** of the following criteria are not eligible for inclusion in this trial.

1. Participant has received prior treatment with any PI3K, mTOR, or AKT inhibitor.
2. Participant with known hypersensitivity to alpelisib or fulvestrant, or to any of the excipients of alpelisib or fulvestrant.
3. Participant has had major surgery within 14 days prior to trial treatment start and/or has not recovered from major side effects.
4. Participant with inflammatory breast cancer at screening.
5. Participant with an established diagnosis of diabetes mellitus type I or not controlled type II (based on fasting glucose [FG] and HbA1c, see inclusion [criterion 8](#))
6. Participant with impairment of gastrointestinal function or gastrointestinal disease that may significantly alter the absorption of the trial treatments (e.g., ulcerative diseases, uncontrolled nausea, vomiting, diarrhea, malabsorption syndrome, or small bowel resection) based on investigator discretion.
7. Participant has currently documented pneumonitis/interstitial lung disease (the chest Computerized Tomography (CT) scan performed at baseline for the purpose of tumor assessment should be reviewed to confirm that there are no relevant pulmonary complications present).
8. Participant with Child Pugh score B or C.
9. Participant with uncontrolled hypertension defined by a Systolic Blood Pressure ≥ 160 mmHg and/or Diastolic Blood Pressure ≥ 100 mmHg, with or without anti-hypertensive medication. Initiation or adjustment of antihypertensive medication(s) is allowed prior to screening.
10. Participant with clinically significant, uncontrolled heart disease and/or recent cardiac events including any of the following:
 - History of angina pectoris, coronary artery bypass graft, symptomatic pericarditis, or myocardial infarction within 6 months prior to the start of trial treatment
 - History of documented congestive heart failure (New York Heart Association functional classification III-IV)
 - History of Left Ventricular Ejection Fraction $< 50\%$
 - Clinically significant cardiac arrhythmias, (e.g., ventricular tachycardia), complete left bundle branch block, high grade atrioventricular (AV) block (e.g. bifascicular block, Mobitz type II and third degree AV block without pacemaker in place)
 - Long QT syndrome, family history of idiopathic sudden death or congenital long QT syndrome, or Fredericia QT correction formula (QTcF) > 470 msec at screening
11. Participant with any other concurrent severe and/or uncontrolled medical condition that would, in the investigator's judgment, contraindicate participant participation in the clinical trial (e.g., chronic active hepatitis, [testing not mandatory unless required by local regulations or requirements] confirmed pneumonitis etc.).
12. Participant is currently receiving any of the following medications and cannot be discontinued 7 days prior to the start of the treatment:
 - Strong cytochrome P (CYP)3A4 inducers

- Inhibitors of breast cancer resistance protein (BCRP)

13. Participant has a history of acute pancreatitis within 1 year of screening or past medical history of chronic pancreatitis.

14. Participant with unresolved osteonecrosis of the jaw.

15. Participant has a history of severe cutaneous reactions like Stevens-Johnson-Syndrome, Erythema Multiforme, or Toxic Epidermal Necrolysis, or Drug Reaction with Eosinophilia and Systemic Symptoms.

16. Participant with evidence of disease progression during the pre-trial induction therapy and prior to first dose of alpelisib.

17. Participant has received radiotherapy \leq 4 weeks or limited field radiation for palliation \leq 2 weeks prior to trial treatment initiation, and who has not recovered to grade 1 or better from related side effects of such therapy (with the exception of alopecia).

18. Participant is currently receiving or has received systemic corticosteroids \leq 2 weeks prior to starting trial treatment, or who have not fully recovered from side effects of such treatment.

Note: The following uses of corticosteroids are permitted: single doses, topical applications (e.g., for rash), inhaled sprays (e.g., for obstructive airways diseases), eye drops or local injections (e.g., intra-articular).

19. Participant participated in a prior investigational study within 30 days prior to the start of trial treatment or within 5 half-lives of the trial treatment, whichever is longer.

20. Participant has not recovered from all toxicities related to prior anticancer therapies to NCI CTCAE version 4.03 Grade \leq 1. Exception to this criterion: participants with any grade of alopecia are allowed to enter the trial.

21. Participant has a concurrent malignancy or malignancy within 3 years of start of trial treatment, with the exception of adequately treated, basal or squamous cell carcinoma, non-melanomatous skin cancer, or curatively resected cervical cancer.

22. Participant has central nervous system (CNS) involvement which was not previously treated and not fulfilling the following 3 criteria to be eligible for the trial:

- Completed prior therapy (including radiation and/or surgery) for CNS metastases \geq 28 days prior to the start of trial entry and
- CNS tumor is clinically stable at the time of screening and
- Participant is not receiving steroids and/or enzyme inducing anti-epileptic medications for brain metastases.

23. Participant has a known history of Human Immunodeficiency Virus infection (testing not mandatory unless required by local regulations or requirements).

24. Participant is not able to understand and to comply with trial instructions and requirements, including oral administration of trial treatment.

25. Participant is a nursing (lactating) or pregnant woman as confirmed by a positive serum (hCG) test prior to initiating trial treatment.

26a. Participant is a woman of child-bearing potential defined as all women physiologically capable of becoming pregnant, unless they are using highly effective methods of contraception during trial treatment and at least for 2 years after the last dose of any trial treatment. Highly effective contraception methods include:

- Total abstinence (when this is in line with the preferred and usual lifestyle of the participant). Periodic abstinence (e.g., calendar, ovulation, symptothermal, post-ovulation methods) and withdrawal are not acceptable methods of contraception
- Female sterilization (have had surgical bilateral oophorectomy with or without hysterectomy), total hysterectomy or bilateral tubal ligation at least 6 weeks before taking trial treatment. In case of oophorectomy alone, only when the reproductive status of the woman has been confirmed by follow up hormone level assessment
- Male sterilization (at least 6 months prior to screening). For female participants on the trial the vasectomized male partner should be the sole partner for that participant

Note: Hormonal contraception is contraindicated for patients with ER positive breast cancer, therefore it is not to be considered as a contraception method for the trial.

Note: Women are considered postmenopausal and not of child bearing potential if they have had 12 months of natural (spontaneous) amenorrhea with an appropriate clinical profile (i.e., age appropriate, history of vasomotor symptoms. Women are considered not of child bearing potential if they are post-menopausal or have had surgical bilateral oophorectomy (with or without hysterectomy), total hysterectomy, or bilateral tubal ligation at least 6 weeks before starting trial treatment. In the case of oophorectomy alone, only when the reproductive status of the woman has been confirmed by follow up hormone level assessment is she considered not of child bearing potential.

If local regulations to prevent pregnancy deviate from the contraception methods listed above, local regulations apply and will be described in the ICF.

27. Participant is a sexually active male unwilling to use a condom during intercourse while taking trial treatment, and for 2 years after the last dose of trial treatment. A condom is required for all sexually active male participants to prevent them from fathering a child AND to prevent delivery of trial treatment via seminal fluid to their partner. In addition, male participants must not donate sperm during the trial and up to the time period specified above.

28. Participants with active infections, including a COVID-19-related diagnosis.

6 Treatment

6.1 Trial treatments

Participants will be administered alpelisib 300 mg daily (2×150 mg film-coated tablets) for 12 cycles of 28 days and fulvestrant 500 mg administered intramuscularly on Cycle 1, Day 1 and Cycle 1, Day 15, and on Day 1 of each cycle thereafter until Cycle 12 (see [Table 6-1](#)).

Table 6-1 Trial treatments

Drugs	Pharmaceutical Form and route of administration	Dose	Frequency and/or regimen	MAH
Alpelisib (Piqray®)	Film coated tablet for oral use	300 mg	Daily (continuous) starting Cycle 1, Day 1	Novartis
Fulvestrant (Faslodex®)	Injection for intra-muscular administration	500 mg	Days 1 and Day 15 on Cycle 1 and Day 1 at each cycle thereafter	AstraZeneca AB

MAH= Marketing Authorization Holder

6.1.1 Additional trial treatments

Depending on menopausal status, women participants may be prescribed goserelin as co-therapy with alpelisib and fulvestrant to induce OFS (see [Table 6-2](#)).

Table 6-2 Co-therapies

Drugs	Pharmaceutical Form and route of administration	Dose	Frequency and/or regimen
Goserelin	Injection for intra-muscular administration	3.6 mg	Starting Cycle 1, Day 1 and Day 1 at each cycle thereafter

6.1.2 Treatment arms/group

All participants enrolled within this trial will receive the same treatment.

6.1.3 Treatment duration

The planned duration of treatment is 12 cycles of 28 days. Participants may be discontinued from treatment earlier than the planned treatment duration due to unacceptable toxicity, disease progression and/or decision made at the discretion of the investigator or the participant.

6.2 Other treatment(s)

6.2.1 Concomitant therapy

6.2.1.1 Permitted concomitant medications

The use of any concomitant medications/non-drug therapies deemed necessary to treat AEs, manage cancer symptoms, concurrent diseases and supportive care agents, such as pain medications, anti-emetics and anti-diarrheal are allowed, except if specifically prohibited (See [Section 6.2.2 "Prohibited medication"](#)).

All medications, procedures, and significant non-drug therapies (including vitamins, physical therapy, herbal/natural medications and blood transfusions) administered within 30 days prior to the start of trial treatment must be recorded on the appropriate electronic Case Report Form.

The investigator should instruct the participant to notify the trial site about any new medications and/or non-drug therapies/procedures he/she takes after signing the informed consent. Each concomitant drug must be individually assessed against all exclusion criteria/prohibited medication. If in doubt, the investigator should contact the Novartis medical monitor before randomizing a participant or allowing a new medication to be started. If the participant is

already enrolled, contact Novartis to determine if the participant should continue participation in the trial.

Oral anti-diabetics

Participants who develop hyperglycemia during the trial should be treated according to the ADA (American Diabetes Association) guidance.

Consultation with a diabetologist or healthcare provider experienced in the management of hyperglycemia is highly recommended for better assessment and management of alpelisib-induced hyperglycemia. It is recommended to start treatment with metformin, however SGLT2 inhibitors may be a suitable alternative or add-on therapy to metformin. SGLT2 inhibitors are a class of diabetic medications that improve hyperglycemia primarily by promoting urinary glucose excretion.

In the SOLAR-1 study, among the 284 participants who were randomized to receive alpelisib plus fulvestrant, 190 participants (67%) developed hyperglycemia, with 18 patients (6%) discontinuing alpelisib treatment due to hyperglycemia, as of 30-Sep-2019.

Among those with hyperglycemia, 166 participants received concomitant anti-diabetic medications, primarily consisting of metformin (87%). However, in addition to metformin, 6 participants also received an SGLT2 inhibitor, consisting of empagliflozin, ipragliflozin, or dapagliflozin. All 6 participants had ≥ 1 risk factor at baseline for developing hyperglycemia, defined as prediabetes ($n = 4$; 1 of whom had documented history of type 2 diabetes), diabetes ($n = 2$), and obesity ($n = 2$). The most severe hyperglycemia in these participants was grade (G) 3 ($n = 5$). After initiating an SGLT2 inhibitor, all subsequent hyperglycemia events were G 1/2, except one G 3 event with steroids as a confounding factor. The duration of alpelisib ranged from 9.5 to 27.7 months in these 6 participants who discontinued alpelisib; and notably, 2 participants were continuing to receive alpelisib after 37.0 and 40.0 months, respectively. None of the 6 participants discontinued alpelisib due to hyperglycemia.

Based on these data, participants may benefit from the initiation of an SGLT2 inhibitor with metformin, which is available as a single oral combination pill or as two separate medications. Particularly in participants with at least one risk factor for the development of severe hyperglycemia, defined as prediabetes/diabetes, and/or obesity ($BMI \geq 30$), and/or age ≥ 75 years, early or prophylactic initiation of an SGLT2 inhibitor alone or in combination with metformin may help to reduce the incidence and frequency of severe hyperglycemia events. The decision to initiate an SGLT2 inhibitor alone or in combination with metformin prophylactically or at the onset of hyperglycemia (first fasting glucose level above the normal range) is at the discretion of the investigator. Since SGLT2 inhibitors may increase the risk of euglycemic diabetic ketoacidosis, serum ketones levels will be assessed throughout the trial in participants treated with SGLT2 inhibitors at screening, Day 1 of each cycle, and at EOT. For additional details on management of alpelisib induced hyperglycemia, please refer to [Section 6.5.1.3](#) “Guidelines for the treatment of alpelisib induced hyperglycemia”.

Participants receiving oral anti-diabetics which are predominantly metabolized by CYP2C9 and CYP2C8, including but not limited to, repaglinide, rosiglitazone, glipizide and tolbutamide, should be monitored with respect to their effectiveness as alpelisib was found to be an inducer of CYP2C9 in vitro.

Gastric protection agents

Alpelisib is characterized by a pH-dependent solubility but can be co-administered with acid reducing agents (e.g. proton-pump inhibitors, H2-antagonists and antacids), as long as it is taken after food. In a joint food effect and acid reducing drug-drug interactions (DDI) study, food exhibited a more pronounced effect on the solubility of alpelisib than the effect of gastric pH value leading to a net decrease in area under the curve of on average by 21% when administered after a meal.

Palliative radiotherapy

Local radiotherapy for analgesic purposes or for lytic lesions at risk of fracture may be carried out if required. Participants requiring initiation of palliative radiotherapy during the course of the trial should be assessed by appropriate image modalities to exclude disease progression per RECIST 1.1 and the reason for its use must be clearly documented. If disease progression is documented, the participant should discontinue trial treatment. No dose modification of trial treatment is needed during radiotherapy.

Hematopoietic growth factors

Hematopoietic growth factors may be used according to American Society of Clinical Oncology guidelines.

Corticosteroids

Chronic dosing of high levels of corticosteroids such as dexamethasone and prednisone may prolong or aggravate hyperglycemia (steroid-induced diabetes). Hyperglycemia is a common adverse event for PI3K inhibitors like alpelisib, so corticosteroids should therefore be used with caution and participants should be closely monitored.

Rash Management

Prophylactic use of antihistamines could be considered, refer to [Section 6.5.1.2](#) “Guidelines for the treatment of trial drug induced skin toxicity”.

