6.2.2 Prohibited medication

The following medications are prohibited during combined alpelisib plus fulvestrant treatment in this trial (see in [Appendix 2](#) "Prohibited Medication", this list is not comprehensive and is only meant to be used as a guide. Please contact the medical monitor with any questions):

- **Strong inducers of CYP3A4:** Avoid co-administration of alpelisib with a strong CYP3A4 inducer as it could potentially reduce the effectiveness of alpelisib, refer to [Table 16-2](#) "List of prohibited strong inducers of CYP3A".
- **Inhibitors of BCRP:** Avoid the use of BCRP inhibitors in participants treated with alpelisib. If unable to use alternative drugs, closely monitor for increased adverse reactions, refer to [Table 16-3](#) "List of prohibited BCRP inhibitors".
- **Other investigational and antineoplastic therapies.**
- **Hormonal contraception:** hormonal contraception is contraindicated for patients with ER positive breast cancer, therefore it is not to be considered as contraception method for the trial.

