9.1 Discontinuation and completion

9.1.1 Trial treatment discontinuation and trial discontinuation

Discontinuation of trial treatment for a participant occurs when trial treatment is stopped earlier than the protocol planned duration and can be initiated by either the participant or the investigator. Participants who discontinue trial treatment will be prematurely withdrawn from the trial.

The investigator must discontinue trial treatment for a given participant if he/she believes that continuation would negatively impact the participant's well-being.

Trial treatment must be discontinued under the following circumstances:

- Participant/guardian decision
- Use of prohibited treatment as per recommendations in the prohibited treatment section
- Any situation in which trial participation might result in a safety risk to the participant

If discontinuation of trial treatment occurs, the investigator should make a reasonable effort to understand the primary reason for the participant's premature discontinuation of trial treatment and record this information.

Whenever possible, participants discontinued early for any reason, should be requested to complete the assessments planned in EOT visit.

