16.1.2 Prohibited Medication

Strong inducers of CYP3A4

This list of CYP inducers was compiled from the University of Washington's Drug Interaction Database (Updated November 2020). This list is only meant to be used as a guide.

Table 16-2 List of prohibited strong inducers of CYP3A

Category	Drug Name
Strong CYP3A Inducers	Apalutamide, Avasimibe ¹ , Carbamazepine, Enzalutamide, Ivosidenib, Lumacaftor, Mitotane, Phenobarbital, Phenytoin, Rifapentine, Rifampin (Rifampicin), St. John's wort (hypericum perforatum) ¹

¹ Herbal product

Inhibitors of BCRP

The table encompasses only drugs and molecular entities for which inhibition of BCRP has been investigated and/or formally shown *in vivo* in a clinical DDI study. Please note that this is not an exhaustive list and only meant to be used as a guide. When in doubt, refer to the prescribing information of the drug to assess whether a potential for BCRP inhibition is described.

Table 16-3 List of prohibited BCRP inhibitors

Category	Drug Name
BCRP inhibitors - Evidence for DDI potential shown in vivo	Atazanavir/ritonavir ^{1,2} , Elvitegravir/cobicistat ^{1,2} , Lopinavir/ritonavir ^{1,2} , Tipranavir/ritonavir ^{1,2} , Curcumin ^{1,2} , Cyclosporine ^{1,2} , Daclatasvir ^{1,2} , Eltrombopag ^{1,2} , Gefitinib ² , Lapatinib ¹ , Ledipasvir ² , Pantoprazole ^{1,2} , Paritepravir ² , Tipranavir ²

¹ Lee et al 2015

² Novartis PK Sciences DDI List (January, 2018)

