E26	Participant is a woman of child-bearing potential defined as all women physiologically capable of becoming pregnant, unless they are using highly effective methods of contraception during trial treatment and at least for 2 years after the last dose of any trial treatment. Highly effective contraception methods include: see Protocol definition	Include in all analyses	49
E27	Participant is a sexually active male unwilling to use a condom during intercourse while taking trial treatment, and for 2 years after the last dose of trial treatment. A condom is required for all sexually active male participants to prevent them from fathering a child AND to prevent delivery of trial treatment via seminal fluid to their partner. In addition, male participants must not donate sperm during the trial and up to the time period specified above	Include in all analyses	49
E28	Participants with active infections, including a COVID-19-related diagnosis	Include in all analyses	49
S1	Study medication not administered	Exclude from safety analyses	5
O1	Study drug related toxicity triggering a dose modification, as per protocol, and participant receives the incorrect dose	Include in all analyses	49
O2	Study drug related toxicity triggering a dose interruption, as per protocol and participant not discontinued from treatment	Include in all analyses	49
O3	Participant concomitantly administered with a strong inducer of CYP3A or inhibitors of BCRP, as per protocol	Include in all analyses	49
O4	Missed questionnaires or e-diary, as per protocol	Include in all analyses	49

Table 5-2 Code Text

Code	Code text
5	Exclude from safety analyses

8	Exclude from all analyses
49	Include in all analyses

6 Reference

Fayers PM (2001). Interpreting quality of life data: population-based reference data for the EORTC QLQ-C30. *Eur J Cancer*; 37(11):1331-4.

ICH E9(R1) Harmonized Guideline: addendum on estimands and sensitivity analysis in clinical trials to the guideline on statistical principles for clinical trials. Final version on 20 November 2019.

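### Protocol 6.2.1.1 permits proton-pump inhibitors without excepting pantoprazole, which Table 16-3 prohibits, and 6.2.2 and 9.1.1 leave the consequence of its use unclear

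*Protocol*

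**What the plan says.** Protocol 6.2.1.1 opens with a general rule: concomitant drugs needed for the participant's care "are allowed, except if specifically prohibited", with a pointer to 6.2.2. It adds that "Each concomitant drug must be individually assessed against all exclusion criteria/prohibited medication", and that doubtful cases go to the sponsor.

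Later in the same section, the paragraph on gastric protection agents says alpelisib "can be co-administered with acid reducing agents (e.g. proton-pump inhibitors, H2-antagonists and antacids", on condition that the dose follows food.

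Section 6.2.2 puts BCRP inhibitors under a lead sentence that calls the listed drugs prohibited. Its bullet on them says to avoid them, and then: "If unable to use alternative drugs, closely monitor for increased adverse reactions". The bullet refers to Table 16-3 in 16.1.2, whose title calls the listed inhibitors prohibited and which includes "Pantoprazole".

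Section 9.1.1 gives the circumstances in which trial treatment must be discontinued. One is "Use of prohibited treatment as per recommendations in the prohibited treatment section". The same section says that participants who discontinue trial treatment are withdrawn from the trial.

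SAP 2.3.2.5 treats use of any substance in Protocol 16.1.2 as a protocol deviation. SAP Table 5-1 lists deviation O3, "Participant concomitantly administered with a strong inducer of CYP3A or inhibitors of BCRP, as per protocol", with code 49, which keeps the participant in all analyses.

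**The concern.** Someone who consults the protocol about a participant on pantoprazole can reach different answers from different pages. The gastric-protection paragraph names the class, discusses a food and acid-reducer interaction study, and sets one condition. A reader could fairly take the interaction question as settled there. Table 16-3 says the drug is prohibited. A reader who reaches the table still cannot tell whether the consequence is close monitoring or the end of trial treatment.

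Two things are at stake. The first is safety: the documents should give one clear instruction about a drug they list for its interaction potential. The second is consistency. If investigators resolve the question differently, then the recorded deviations, the reasons for discontinuation and the time on treatment will partly reflect how each of them read the protocol.

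**Working it through.** No arithmetic applies, and the plan has no figure to reproduce. The check sets the provisions side by side.

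| Place | Covers | Status given | Consequence stated |
|---|---|---|---|
| Protocol 6.2.1.1, opening | All concomitant drugs | Allowed unless specifically prohibited; check each drug | Doubtful cases go to the sponsor |
| Protocol 6.2.1.1, gastric protection | Proton-pump inhibitors as a class | May be given, alpelisib after food | None |
| Protocol 6.2.2, lead sentence | BCRP inhibitors | Prohibited | None |
| Protocol 6.2.2, bullet | BCRP inhibitors | Avoid | Close monitoring if no alternative can be used |
| Protocol Table 16-3 | Pantoprazole by name | Prohibited | None |
| Protocol 9.1.1 | Prohibited treatment | Not applicable | Trial treatment stops, subject to the recommendations in the prohibited-treatment section |
| Protocol 5.2, exclusion 12 | BCRP inhibitors at entry | Not eligible if the drug cannot be stopped 7 days before treatment | Before treatment only |
| SAP 2.3.2.5 and Table 5-1 (O3) | Substances in 16.1.2; BCRP inhibitors | Protocol deviation | Kept in all analyses |

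**Step 1: is pantoprazole permitted?** The general carve-out and the drug-by-drug check lead to Table 16-3, so the better reading is that the specific prohibition governs. The class permission, however, contains no exception and no pointer to the table. The paragraph on herbal products in 6.2.1.2 shows that the authors add such exceptions elsewhere: it makes the permission subject to explicit prohibitions, names curcumin and cites Table 16-3.

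**Step 2: can the reader find the list?** The lead sentence of 6.2.2 sends the reader to Appendix 2 for prohibited medication. Appendix 2 (16.2) is about liver events. The list is in 16.1.2, within Appendix 1, whose title refers to permitted medication to be used with caution. The bullet itself cites Table 16-3 correctly.

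**Step 3: what follows from use?** Section 9.1.1 is mandatory in form but defers to the recommendations of the prohibited-treatment section. Section 6.2.2 says both that these drugs are prohibited and that they may be used with monitoring if alternatives cannot be. Through the lead sentence and the title of Table 16-3, 9.1.1 requires discontinuation. Through the bullet, it does not. The documents do not choose between these readings.

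**Step 4: does it reach the analysis?** O3 and the deviation for exclusion 12 (E12) both carry code 49, so neither removes anyone. Retention on remote monitoring is measured among participants still on treatment, so a participant who stops leaves the denominator and is not counted as a failure. The SAP introduction says the study ended early for low enrollment and that data will be listed only. What remains exposed is the record of deviations, discontinuation reasons and time on treatment.

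**The case against.** The strongest reply is that the protocol supplies its own order of precedence. Section 6.2.1.1 yields to specific prohibitions, the introduction to Appendix 1 says the same, and pantoprazole is specifically listed. The gastric-protection sentence deals with pH and solubility and does not address BCRP. This largely stands: a careful reader who follows the carve-out will find the prohibition. It does not clear the paragraph of misleading by omission, and it does not answer what happens after use.

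Several stronger readings are tempting, and the documents do not support them:

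- A reader might infer that a participant on pantoprazole is forced off trial treatment. Section 9.1.1 is qualified by 6.2.2, which foresees monitored use, and 6.2.1.1 offers a case-by-case route through the sponsor. Discontinuation is one available reading and no more.
- A reader might infer that district nurses prescribe such drugs away from the site. Section 8.6.2 has them giving concomitant medication that the investigator has prescribed, and it leaves trial-related decisions with the investigator.
- A reader might infer that exclusion 12 or SAP deviation O3 adds a further conflict. Exclusion 12 is an entry rule, conditional on the drug not being stoppable. O3 follows the protocol and excludes nobody.
- A reader might infer an effect on retention or PFS. None is shown. The retention denominator is limited to participants on treatment, PFS is to be listed by patient, and the number of pantoprazole users is unknown.

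**Conclusion.** The inconsistency is confirmed and is worth correcting. A class permission omits an exception that the prohibited list requires, and the consequence of using a listed BCRP inhibitor is ambiguous between monitoring and discontinuation with withdrawal from the trial.

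Its size cannot be given as a number. The documents state no frequency of use, so the number affected could be anything from none to all of those enrolled. For scale only, one participant among the approximately 20 planned is 1/20 = 5%. That describes the sample and estimates no effect.

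The conclusion rests on two assumptions. Pantoprazole is taken to be a proton-pump inhibitor, which is general pharmacology and is not spelled out in the protocol. No other document, such as the operational manual, is taken to resolve the point. The conclusion does not depend on which of the two rules the sponsor intended.

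**What to change.** Reconcile Protocol 6.2.1.1, 6.2.2, Table 16-3 and 9.1.1 so that each listed agent has one status and one stated consequence. In particular:

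- Add a cross-reference to Table 16-3 in the gastric-protection paragraph of 6.2.1.1.
- Make the lead sentence and the BCRP bullet of 6.2.2 agree, and correct the appendix reference.
- State in 9.1.1 what use of a listed BCRP inhibitor entails, in terms that match 6.2.2.

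The choice of rule belongs to the sponsor. SAP deviation O3 refers back to the protocol and needs no separate change.

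The cost is a wording amendment and a notice to sites, with no new data and no change to the analysis. As the study ended early, the practical gain is now mainly in reporting. SAP 2.3.2.5 still calls for prohibited medications to be tabulated and listed, so the agreed status should be documented before that output is produced.

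If the protocol text is reused for another study, the correction should be made there first.
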